### Termination of Study

After the completion or termination of the study, all relevant study documents and data will be sent to the Sponsor by the CRO. The Investigator will inform the IRB of the end of the study and a certificate of study closure will be issued.

## 16. Publication Plan

Any presentation or publication of data collected as a direct or indirect result of this trial will be considered as a joint publication by the Investigator(s) and the appropriate personnel at the Sponsor's site. Authorship will be determined by mutual agreement. All manuscripts, abstracts or other modes of presentation arising from the results of the study must be reviewed and approved in writing by the Sponsor, prior to submission for publication or presentation. No publication or presentation with respect to the study shall be made until all Sponsor comments on the proposed publication or presentation have been addressed to the Sponsor's satisfaction.

	Protocol 812P413	
	Page 55 of 61	Version 2.0

The detailed obligations regarding the publication of any data, material results, or other information, generated or created in relation to the study shall be outlined in the agreement between each Investigator and the Sponsor or designee.

	Protocol 812P413	
	Page 56 of 61	Version 2.0

1. INTRODUCTION

The purpose of this Statistical Analysis Plan (SAP) is to outline the planned analyses in the study protocol and to provide detailed statistical methods that will be used for the Clinical Study Report (CSR). This SAP is based on Study Protocol 812P413, version 2.0, dated 25Nov2024.

2. STUDY OBJECTIVES AND ENDPOINTS

2.1. Primary Objective and Endpoint

Primary Efficacy		
OBJECTIVES	ENDPOINTS	JUSTIFICATION FOR ENDPOINTS
The primary objective of this study is to evaluate the efficacy of Qelbree as a monotherapy and/or as an adjunctive therapy for ADHD symptoms in adults with ADHD and comorbid mood symptoms as measured by the clinician-rated ADHD Investigator Symptom Rating Scale (AISRS).	Change from baseline in AISRS total score by visit.	The AISRS is a clinician-rated scale that was validated for evaluating ADHD symptoms in adults in clinical trials per criteria outline in the DSM-5. The AISRS has been used in other clinical trials to evaluate the efficacy/safety of ADHD treatments, including the clinical trials of Qelbree in adults (Studies 812P306 and 812P311).

2.2. Secondary Objectives and Endpoints

Secondary Efficacy		
OBJECTIVES	ENDPOINTS	JUSTIFICATION FOR ENDPOINTS
To evaluate the effect of Qelbree as a monotherapy and/or as an adjunctive therapy on Inattention (IA) and Hyperactivity/Impulsivity (HI) symptoms in adults with ADHD and comorbid mood symptoms as measured by the clinician-rated AISRS.	Change from baseline in AISRS Inattention and Hyperactivity/Impulsivity Subscale scores by visit.	The AISRS is a clinician-rated scale that was validated for evaluating ADHD symptoms in adults in clinical trials per criteria outline in the DSM-5. The AISRS has been used in other clinical trials to evaluate the efficacy/safety of ADHD treatments, including the clinical trials of Qelbree in adults (Studies 812P306 and 812P311).
To evaluate the effect of Qelbree as a monotherapy and/or as an adjunctive therapy for ADHD symptoms in adults with ADHD and comorbid mood symptoms as measured by the self-rated ASRSv1.1-SC.	Change from baseline in ASRSv1.1-SC Total score by visit.	In the Race category, the total of the non-white subcategories does not match the overall non-white value. Are there any categories that are not included
To evaluate the effect of Qelbree as a monotherapy and/or as an adjunctive therapy on IA and HI symptoms in adults with ADHD and comorbid mood symptoms as measured by the self-rated ASRSv1.1-SC.	Change from baseline in ASRSv1.1-SC Inattention and Hyperactivity/Impulsivity Subscale scores by visit.	The ASRSv1.1-SC is a self-report scale that was validated for evaluating ADHD symptoms in adults in clinical trials per criteria outline in the DSM-5. The ASRSv1.1-SC and similar endpoints have been used in other clinical trials that evaluated efficacy and safety of ADHD treatments.
To evaluate the effect of Qelbree as a monotherapy and/or adjunctive therapy on global severity of ADHD symptoms in adults with ADHD and comorbid mood symptoms as measured by the clinician-rated CGI-S scale.	Change from baseline in the CGI-S score by visit.	The clinician-rated CGI-S scale is commonly used in most clinical trials, especially ADHD.

Secondary Efficacy		
OBJECTIVES	ENDPOINTS	JUSTIFICATION FOR ENDPOINTS
To evaluate the effect of Qelbree as a monotherapy and/or adjunctive therapy on global change in ADHD symptoms in adults with ADHD and comorbid mood symptoms as measured by the clinician-rated CGI-C scale.	CGI-C score by visit.	The clinician-rated CGI-C scale is commonly used in most clinical trials, especially ADHD.
To evaluate the effect of Qelbree as a monotherapy and/or adjunctive therapy on depressive symptoms in adults with ADHD and comorbid mood symptoms as measured by the clinician-rated Montgomery-Åsberg Depression Rating Scale (MADRS) (SIGMA) and by the self-rated PHQ-8.	Change from baseline in: 
 • MADRS (SIGMA) Total Score at Week 14/EOS • PHQ-8 Total score by visit 	The clinician-rated MADRS (SIGMA) and self-report PHQ-8 are commonly used to assess symptoms of depression in clinical trials.
To evaluate the effect of Qelbree as a monotherapy and/or adjunctive therapy on anxiety symptoms in adults with ADHD and comorbid mood symptoms as measured by the clinician-rated Hamilton Anxiety Rating Scale (HAM-A) (SIGH-A) and the self-rated General Anxiety Disorder 7-item Scale (GAD-7).	Change from baseline in: 
 • HAM-A (SIGH-A) Total score at Week 14/EOS • GAD-7 Total score by visit 	The clinician-rated HAM-A (SIGH-A) and self-report GAD-7 are commonly used to assess symptoms of anxiety in clinical trials.
To evaluate the effect of Qelbree on executive function in adults with ADHD and comorbid mood symptoms as measured by the BRIEF-A, Self-Report.	Change from baseline at Week 14/EOS in BRIEF-A T-score for the: 
 • Global Executive Composite (GEC) • Behavioral Regulation Index (BRI) • Metacognition Index (MI) 	ADHD-associated impairments in executive function in ADHD is well known. The BRIEF-A is a self-report scale that was validated for evaluating global and aspects of executive function in adults with ADHD. It has been administered in other clinical trials that evaluated the efficacy and safety of ADHD treatments.
To evaluate the effect of Qelbree as a monotherapy and/or adjunctive therapy on aspects of functioning in daily life (work productivity and regular activities) as measured by the Work Productivity and Activity Impairment: Specific Health Problem Questionnaire (WPAI:SHP).	Change from baseline in the WPAI:SHP: 
 • absenteeism percentage by visit • presenteeism percentage by visit • work productivity percentage by visit • regular activity percentage by visit 	ADHD-associated functional impairments is well known. The WPAI:SHP is a self-report scale that was validated for evaluating functional impairment in aspects of daily life. It has been administered to assess the impact of ADHD and ADHD treatments on work productivity and regular activities in adults with ADHD.

Secondary Efficacy		
OBJECTIVES	ENDPOINTS	JUSTIFICATION FOR ENDPOINTS
To evaluate the effect of Qelbree on sleep in adults with ADHD and comorbid mood symptoms as measured by the self-rated PSQI.	Change from baseline at Week 14/EOS in the PSQI global score	Sleep and/or circadian-related disturbances (e.g., insomnia, daytime sleepiness, delayed sleep phase disorder) have been documented in participants diagnosed with ADHD and in individuals receiving treatment with psychiatric and psychostimulant medication. The PSQI is commonly used in clinical trials to assess changes in sleep parameters (quality, timing, duration, latency, etc.) and overall daytime functioning.

Secondary Safety		
OBJECTIVES	ENDPOINTS	JUSTIFICATION FOR ENDPOINTS
To evaluate the safety of Qelbree as a monotherapy and/or adjunctive therapy as a monotherapy and/or as an adjunctive therapy in adults with ADHD and comorbid mood symptoms	Safety endpoints are: 
 • Adverse events (AEs) • Change from baseline in blood pressure, pulse rate, and weight • Suicidality using the Columbia Suicide Severity Rating Scale (C-SSRS) 	These endpoints were chosen to assess safety parameters related to caution and/or warnings in Qelbree Prescribing Information.

2.3. Exploratory Objective and Endpoint

Exploratory		
OBJECTIVES	ENDPOINTS	JUSTIFICATION FOR ENDPOINTS

[figure not shown]
Exploratory		
OBJECTIVES	ENDPOINTS	JUSTIFICATION FOR ENDPOINTS

3. STUDY DESCRIPTION

3.1. Study Design

This is a Phase IV, open-label, fully decentralized clinical trial to evaluate the efficacy and safety of Qelbree in adults with ADHD and Mood Symptoms (Figure 1). Participants will complete patient-reported outcome (PRO) measures on the study mobile app after each tele-visit with a qualified, trained rater or assessor (Appendix, Table 2).

Figure 1. Protocol Schema

3.2. Schedule of Procedures and Assessments

The Schedule of Procedures and Assessments for the study is presented in Table 1 of the study protocol and it is in Appendix, Table 2 of this document.

3.3. Study Treatment

3.3.1. Study Treatment Description

Qelbree (viloxazine extended-release capsules) is a selective norepinephrine reuptake inhibitor indicated for the treatment of ADHD in adults and pediatric patients 6 years and older. Qelbree received marketing approval in the US in 2021 for pediatric patients 6-17 years of age, and in 2022 for adults ≥ 18 years of age (Qelbree PI).

3.3.2. Study Treatment Administration

Qelbree (viloxazine extended-release capsules) is supplied in 100 mg, 150 mg, and 200 mg capsules (Qelbree PI).

Participants will be instructed to take Qelbree 200 mg once daily (QD) in the morning during Week 1 and 400 mg QD in the morning during Week 2 onwards until next contact with investigator. The investigator may adjust/titrate dosage in increments of up to 200 mg weekly to the maximum recommended dosage of 600 mg once daily, depending on response and tolerability. At the discretion of the investigator based on tolerability, the subject may be instructed to take total daily dose once daily in the evening.

3.4. Randomization

Not applicable for this study.

3.5. Blinding

This is an open label, non-randomized, study; therefore, treatment blinding is not applicable.

3.6. Sample Size

Approximately 750 participants will be dosed in this study, to obtain 500 completed (through the end of Week 14 of treatment) participants, with an anticipated attrition rate of 33%. There is no consideration for power for the sample size determination in this decentralized, open label study.

4. STUDY VARIABLES

4.1. Primary Efficacy Variable

- The primary efficacy variable is the change from baseline (CFB) in **AISRS Total** score by visit. The AISRS consists of 18 items that directly correspond to the 18 symptoms of ADHD and is further subdivided into two subscales: Inattention (9 items) and Hyperactivity/Impulsivity (9 items). The severity of each symptom is rated on a 4-point scale (0-3; where 0 = None, 1 = Mild, 2 = Moderate, and 3 = Severe) based on participants behavior in the past week. The sum of all 18 items yields the Total score (range 0-54). Higher scores indicate more severe ADHD symptoms. A CFB in AISRS Total score <0 represents a better outcome (reduction in ADHD symptoms).

4.2. Secondary Efficacy Variables

The following are the list of secondary efficacy variables.

- CFB in **AISRS Inattention Subscale** score by visit: The sum of all 9 Inattention items (odd numbered items) yields the Inattention Subscale score (range 0-27). Higher scores indicate more severe Inattention symptoms. A CFB in Inattention Subscale score <0 represents a better outcome (reduction in Inattention symptoms).
- CFB in **AISRS Hyperactivity/Impulsivity Subscale** score by visit: The sum of all 9 Hyperactivity/Impulsivity items (even numbered items) yields the Hyperactivity/Impulsivity Subscale score (range 0-27). Higher scores indicate more severe Hyperactivity/Impulsivity symptoms. A CFB in Hyperactivity/Impulsivity Subscale score <0 represents a better outcome (reduction in Hyperactivity/Impulsivity symptoms).
- CFB in **ASRSv1.1-SC Total** score by visit: The ASRSv1.1-SC consists of 18 items that correspond to the 18 DSM-IV symptoms of ADHD, which are further subdivided into two subscales: Inattention (9 items) and Hyperactivity/Impulsivity (9 items). Participants rate the frequency of each symptom on a 5-point scale (0-4, where 0 = Never, 1 = Rarely, 2 = Sometimes, 3 = Often, and 4 = Very Often) based on participant's experience in the past week. The sum of all 18 items yields the Total score (range 0-72). Higher scores indicate more severe ADHD symptoms. A CFB in ASRSv1.1-SC Total score <0 represents a better outcome (reduction in ADHD symptoms).
- CFB in **ASRSv1.1-SC Inattention Subscale** score by visit: The sum of all 9 Inattention items (Item #1, 2, 3, 4, 7, 8, 9, 10, 11) yields the Inattention Subscale score (range 0-36). Higher scores indicate more severe Inattention symptoms A CFB in Inattention Subscale score <0 represents a better outcome (reduction in Inattention symptoms).
- CFB in **ASRSv1.1-SC Hyperactivity/Impulsivity Subscale** score by visit: The sum of all 9 Hyperactivity/Impulsivity items (Item #5, 6, 12, 13, 14, 15, 16, 17, 18) yields the Hyperactivity/Impulsivity Subscale score (range 0-36). Higher scores indicate more severe Hyperactivity/Impulsivity symptoms. A CFB in Hyperactivity/Impulsivity Subscale score <0 represents a better outcome (reduction in Hyperactivity/Impulsivity symptoms).

- CFB in **CGI-S** score by visit: The CGI-S scale is a single item clinician's rating of the severity of the ADHD symptoms in relation to the clinician's total experience with subjects with ADHD. The CGI-S is a single item evaluated on a 7-point scale with 1 = Asymptomatic, no symptoms, 2 = Borderline, 3 = Mild, 4 = Moderate, 5 = Marked, 6 = Severe, and 7 = Among the most extreme. Successful therapy is indicated by a lower overall score in subsequent testing. A CFB in CGI-S score <0 represents a better outcome (reduction in severity).
- The **CGI-C** score by visit: The CGI-C scale is a single item clinician's assessment of how much the patient's ADHD symptoms have changed (improved, worsened or no change) during treatment relative to his/her baseline state prior to the beginning of treatment. The CGI-C is evaluated on a 7-point scale with 1 = Very much improved, 2 = Much improved, 3 = Minimally improved, 4 = No change, 5 = Minimally worse, 6 = Much worse, and 7 = Very much worse. Successful therapy is indicated by a score <4 in subsequent testing.
- CFB in **MADRS Total** Score at Week 14/EOS: The MADRS consists of 10 items. Each item/symptom is rated on a 7-point scale (0 to 6 continuum, where 0=no abnormality to 6=severe). The sum of all 10 items yields the MADRS Total score (range 0 to 60). A total score ranging from 0-6 indicates that the subject is in the normal range (no depression), a score ranging from 7-19 indicates "mild depression", 20 to 34 indicates "moderate depression", a 35 to 60 indicates "severe depression". A CFB in MADRS Total score <0 represents a better outcome (reduction in depression symptoms).
- CFB in **PHQ-8 Total** Score by visit: The PHQ-8 is a 8-item depression module, which the patient scores each on 4-point Likert scale (0-3), where 0 = not at all; 1 = several days, 2 = more than half the days, and 3 = nearly every day. The sum of all 8 items yields the PHQ-8 Total score (range 0 to 24). A PHQ-8 Total score ≥ 10 indicates major depression and ≥ 20 indicates severe major depression. A CFB in PHQ-8 Total score <0 represents a better outcome (reduction in depression symptoms).
- CFB in **HAM-A Total** Score at Week 14/EOS: The HAM-A consists of 14 items. Each item is rated/scored on a 5-point Likert scale, where 0 = Not present, 1 = Mild, 2 = Moderate, 3 = Severe, and 4 = Very severe. The HAM-A (SIGH-A) Total score is the sum of all 14 items ranging from 0 to 56, where ≤ 17 indicates "mild anxiety severity," 18 to 24 indicates "moderate anxiety severity," 25 to 30 indicates "moderate to severe anxiety severity," and ≥ 31 indicates "severe anxiety." A CFB in HAM-A Total score <0 represents a better outcome (reduction in depression symptoms).
- CFB in **GAD-7 Total** score by visit: The GAD-7 scale is a self-reported 7-item questionnaire for screening and measuring the severity of generalized anxiety disorder. The patient scores each item on 4-point Likert scale, where 0 = Not at all, 1 = Several days, 2 = Over half the days, and 3 = Nearly every day. The GAD-7 Total Score is the sum of all 7 items ranging from 0 to 21, where a total score of 0 to 4 = None/Minimal anxiety, 5 to 9 = Mild anxiety, 10 to 14 = Moderate anxiety, and ≥ 15 = Severe anxiety. A CFB in GAD-7 Total score <0 represents a better outcome (reduction in anxiety symptoms).

WPAI:SHP scales will be derived from these 6 questions:

Q1 = currently employed;

Q2 = hours missed due to specified problem;

Q3 = hours missed other reasons;

Q4 = hours actually worked;

Q5 = degree problem affected productivity while working; where 0 = “My ADHD symptoms had no effect on my work” and 10 = “My ADHD symptoms completely prevented me from working”

[figure not shown]
Q6 = degree problem affected regular activities, other than work at a job; where 0 = “My ADHD symptoms had no effect on my daily activities” and 10 = “My ADHD symptoms completely prevented me from doing my daily activities”

[figure not shown]
- CFB in **WPAI:SHP Absenteeism** percentage by visit: The WPAI:SHP questionnaire consists of 6 items that ask about the number of hours missed from work or regular activities due to the specific health problem, and the degree of impairment while working or performing regular activities. WPAI outcomes are expressed as impairment percentages. Percent work time missed due to problem (absenteeism) is calculated using the following formula: $[Q2/(Q2+Q4)] \times 100$ (range 0 to 100%). A higher percentage indicates greater impairment and less productivity. A CFB in percentage <0 represents a better outcome.
- CFB in **WPAI:SHP Presenteeism** percentage by visit: Percent impairment while working due to problem (presenteeism) is calculated using the following formula: $[Q5/10] \times 100$ (range 0 to 100%). A higher percentage indicates greater impairment and less productivity. A CFB in percentage <0 represents a better outcome.
- CFB in **WPAI:SHP Work Productivity** percentage by visit: Percent overall work impairment due to problem is calculated using the following formula: $[Q2/(Q2+Q4) + ((1 - (Q2/(Q2+Q4))) \times (Q5/10))] \times 100$ (range 0 to 100%). A higher percentage indicates greater impairment and less productivity. A CFB in percentage <0 represents a better outcome.
- CFB in **WPAI:SHP Regular Activity** percentage by visit: Percent activity impairment due to problem is calculated using the following formula: $[Q6/10] \times 100$ (range 0 to 100%). A higher percentage indicates greater impairment and less productivity. A CFB in percentage <0 represents a better outcome.
- **The BRIEF-A** is a standardized 75-item self-rating scale that assesses overall functioning (GEC) and 9 non-overlapping scales among 2 summary index scales (Metacognition Index [MI] and Behavioral Regulation Index [BRI]) that assess aspects of executive function and problems with self-regulation from the perspective of the individual. Raw GEC scores, BRI, MI and their subscales (individual scales) will be converted to T-scores (T-score ≥ 65 is considered abnormally elevated) using Appendix A of the BRIEF-A Professional Manual and change from baseline in T-scores will be calculated. A lower change from baseline GEC T-score (<0) represents a better outcome.
- CFB in **BRIEF-A Global Executive Function (GEC) T-Score** at Week 14/EOS:
Behavioral Regulation Index [BRI]) that assess aspects of executive function and problems with self-regulation from the perspective of the individual. Subjects rate each

[figure not shown]
item on a 3-point scale (1=Never, 2=Sometimes, or 3=Often) based on their experience in past month. The sum of 70 items yields the GEC raw score (range: 70-210).

[figure not shown]
- CFB in the **BRIEF-A Behavioral Regulation Index (BRI)** T-score at Week 14/ EOS: The BRI captures the ability to maintain appropriate regulatory control of one's own behavior and emotional responses. The sum of 30 items yields the BRI raw score (range: 30-90).
- CFB in the **BRIEF-A Metacognitive Index (MI)** T-score at Week 14/ EOS: MI reflects individual's ability to problem solve (includes initiate activity, generate ideas, sustain working memory, plan/organize approaches, monitor success/failure, and organize materials/environment). The sum of 40 items (list can be found in the BRIEF-A manual) yields the MI raw score (range: 40-120).
- CFB in **PSQI Global** score at Week 14/EOS: The PSQI is a 19-item questionnaire that generates a Global score out of which generate 7 component scores (or domains): subjective sleep quality, sleep latency, sleep duration, habitual sleep efficiency, sleep disturbances, use of sleep medication, and daytime dysfunction over the last month. The individual rates each of these 7 areas of sleep. Scoring of the answers is based on a 0 to 3 scale, where a score of 3 reflects the negative extreme on the Likert Scale and 0 better on the individual scales. The sum of all the 7 components scores yields the global score (range 0-21); a global sum of "5" or greater indicates a "poor" sleeper.

4.3. Exploratory Efficacy Variables

5. STATISTICAL CONSIDERATIONS

5.1. General Statistical Methods

All statistical analysis will be performed using SAS version 9.4 or higher. All statistical analyses will be presented using descriptive statistics. Summary statistics for continuous variables will include sample size (N), mean, median, standard deviation, interquartile range (Q1 and Q3), minimum, and maximum. Standard error may be added if it is needed for the display and interpretation of some efficacy results. Summary statistics for categorical variables will be presented in terms of frequencies and percentages. Participant data listing to support summaries will be provided.

Unscheduled measurements (unless defined as baseline or otherwise specified) will be excluded from descriptive statistics performed by visits in summary tables but will be included in data listings and other analyses that not performed by visit. For assessments that are repeated, unless otherwise specified, the non-missing values from the first assessment will be used for generating summary statistics.

Mean (\pm SE) profiles and Mean (\pm SE) CFB for AISRS total score, MADRS, HAM-A and GAD-7 will be plotted by visit.

5.2. Baseline Definitions

Baseline is defined as the last non-missing assessment measured prior to the start of SM.

5.3. Analysis Populations

Safety Population: This includes all subjects who received at least one dose of Qelbree.

Full Analysis Set: This includes a subset of subjects in the Safety Population who have a valid AISRS at baseline (prior to first dose) and at least one valid AISRS post-baseline assessment.

5.4. Adjustments for Covariates

No covariates adjustments analyses are planned for this study.

5.5. Hypotheses and Test Statistic

No formal hypotheses are planned for this study.

5.6. Handling of Missing data

5.6.1. Missing Efficacy Endpoints

Missing efficacy variables will be handled using the following rules:

- For AISRS Total Score and subscales Inattention & Hyperactivity/Impulsivity, if more than 3 items are missing then the total score will be set to missing. If ≤ 3 items are missing then the values for the missing items will be imputed using the mean of the non-missing items rounded to the nearest integer.
- For ASRSv1.1 Total Score and subscales Inattention & Hyperactivity/Impulsivity, if more than 3 items are missing then the total score will be set to missing. If ≤ 3 items are missing then the values for the missing items will be imputed using the mean of the non-missing items rounded to the nearest integer.

- For the following scales, if 1 of the individual item score is missing, either the total or subscale score will be set to missing. GAD-7 Total Score, HAM-A Total Score, BRIEF-A GEC Total Raw Score, BRIEF-A BRI Raw Score, BRIEF-A MI Raw Score, all the 9 non-overlapping BRIEF-A subscales.
- For WPAI:SHP, if Q1 = No, questions 2-5 are not applicable. If Q1 = Yes, questions 2 through 6 (Q2-Q6) are not allowed to be missing. If these questions are missing, then any scores calculated using the missing questions are also set to missing. For example, Absenteeism (hours) is derived from questions 2 and 4 (Q2 and Q4), if either Q2 or Q4 is missing, then Absenteeism will be set to missing. The same logic applies to the three-remaining score.
- For PSQI, questions 1 through 9 (Q1-Q9) are not allowed to be missing. If these questions are missing, then any scores calculated using missing questions are also set to missing. For example, “Sleep Latency” is derived based on Q2 and Q5a, if either Q2 or Q5a is missing, the “Sleep Latency” score will be set to missing, and the same logic applies to the other remaining scales. If a range is given for an answer (for example, ‘30 to 60’ is written as the answer to Q2, minutes to fall asleep), use the mean.

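### One blank item in 70 sets the BRIEF-A GEC to missing, while the SAP imputes up to 3 of 18 blanks on the ASRS and AISRS; prorating would be a cheap, low-priority improvement

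*SAP*

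**What the plan says.** SAP 5.6.1 (Missing Efficacy Endpoints) has two kinds of item rule that matter here.

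- **No tolerance.** "For the following scales, if 1 of the individual item score is missing, either the total or subscale score will be set to missing". Besides the GAD-7 and HAM-A totals, the list covers "BRIEF-A GEC Total Raw Score, BRIEF-A BRI Raw Score, BRIEF-A MI Raw Score, all the 9 non-overlapping BRIEF-A subscales".
- **Tolerance of three.** For the AISRS, and in the same terms for the ASRSv1.1-SC, "if more than 3 items are missing then the total score will be set to missing". With three or fewer blanks, "the values for the missing items will be imputed using the mean of the non-missing items rounded to the nearest integer".

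SAP 4.2 gives the length of the BRIEF-A scores: "The sum of 70 items yields the GEC raw score (range: 70-210"), with 30 items for the BRI and 40 for the MI. The AISRS and ASRS have 18 items each.

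The schedule (Protocol Table 1, repeated as SAP Table 2) places BRIEF-A at Televisit 1b and at Week 14/EOS, not at Week 4 or Week 9. SAP 7.2 lists the endpoint as change in T-score at Week 14/EOS for GEC, BRI and MI. The SAP gives no reason for the different tolerances.

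**The concern.** The longest questionnaire in the study has the strictest rule. One unanswered item removes the GEC and the index it belongs to, and with them 69 valid answers. The ASRS, also a self-report completed in the study app at the same two visits, keeps its score with 3 of 18 items blank.

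There is also no scheduled fallback. Baseline is the last non-missing value before dosing (SAP 5.2), but only one BRIEF-A is scheduled before dosing, and the endpoint uses only the Week 14/EOS form.

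At stake is the number of participants behind three secondary summaries, on top of the 33% attrition already planned for. If people who skip items differ from those who do not, the executive-function change would also describe a somewhat selected group.

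**Working it through.** **Inputs from the documents**

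- BRIEF-A scale lengths (Protocol 9.2.2.4): BRI = 8 + 6 + 10 + 6 = 30; MI = 8 + 8 + 10 + 6 + 8 = 40; GEC = 30 + 40 = 70. These agree with SAP 4.2. The other 5 of the 75 items do not enter the GEC.
- Blanks tolerated: GEC 0 of 70; ASRS and AISRS totals 3 of 18 = 16.7%. One blank is 1/70 = 1.4% of the GEC.
- Sample size (SAP 3.6): 750 dosed, 500 completed, 33% attrition. Check: 500/0.67 = 746.3, so 747 against 750; forward, 750 × 0.67 = 502.5 against 500. The plan's figures agree, and 500 is used below as the base for counts.

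**Assumed input.** The documents give no item-blank rate *p*, so a range is shown.

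**Independent blanks.** One form of *m* items is lost with probability q = 1 − (1 − p)^m. A change score needs both forms, so the loss is 1 − (1 − q)² = 1 − (1 − p)^(2m); for the GEC the exponent is 140.

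| p per item | GEC change lost | of 500 | MI lost | BRI lost |
|---|---|---|---|---|
| 0.01% | 1.4% | 7 | 0.8% | 0.6% |
| 0.05% | 6.8% | 34 | 3.9% | 3.0% |
| 0.1% | 13.1% | 65 | 7.7% | 5.8% |
| 0.2% | 24.4% | 122 | 14.8% | 11.3% |

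Under the three-blank rule for 18 items, the loss stays below 0.001% at all of these rates.

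**Clustered blanks.** If a fraction *f* of forms contains at least one blank, independently at the two visits, the loss is 1 − (1 − f)². For f = 1%, 2%, 5% and 10% this gives 2.0%, 4.0%, 9.8% and 19.0% (10, 20, 49 and 95 of 500). If the same people leave blanks at both visits, the loss is smaller and approaches *f*.

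**Precision.** The standard error grows by 1/√(1 − loss). A 1.4% loss gives 1/√0.986 = 1.007, a 13.1% loss gives 1/√0.869 = 1.07, and a 24.4% loss gives 1/√0.756 = 1.15.

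**What one blank costs if it is filled in.** Items score 1 to 3, so one imputed item can be wrong by at most 2 raw points. The GEC range is 210 − 70 = 140 points, and 2/140 = 1.4%.

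**Under the proposed 90% threshold.** The BRI needs 27 of 30 items (3 blanks allowed) and the MI 36 of 40 (4 allowed). Any form with at most 3 blanks among the 70 therefore keeps its GEC. The chance of losing the change score is then at most about 0.0002% at p = 0.1% and 0.0026% at p = 0.2%.

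**The case against.** **The app may prevent blanks.** BRIEF-A is completed in the study app (Protocol 6.1.2, 6.3 and Table 1 footnote 9), responses are captured directly (11.1), and the database has programmed completeness checks (11.4). This makes the low end of the range at least as relevant as the high end. It does not settle the matter. No section says that a BRIEF-A form cannot be submitted with a blank, and SAP 5.6.1 provides for missing items on other app questionnaires (ASRS, WPAI:SHP, PSQI).

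**The AISRS is a weak comparator.** This stands: it is a clinician interview. The ASRS is the fair comparison, and the contrast with it remains.

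**BRIEF-A is not singled out.** This also stands. The GAD-7 and HAM-A have the same rule, and the WPAI:SHP and PSQI have similar ones. A reader might infer that the SAP contradicts itself, but different scales may have different scoring rules. BRIEF-A is only the most exposed, because of its length. The SAP rule might even follow the BRIEF-A manual, which cannot be checked from the documents.

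**Larger losses are conceivable.** At p = 0.5% the formula gives 50%. A reader might conclude that half the GEC scores are at risk, but that needs about 30% of forms at each visit to contain a blank (1 − 0.995^70 = 29.6%), and nothing in the documents supports this.

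**Selection is conjecture.** More inattentive participants may skip more items, but no direction or size can be shown. If blanks do cluster in certain people, the clustered figures are the more relevant ones.

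**Conclusion.** The rule is clear and prespecified, but poorly matched to a 70-item instrument. The loss cannot be determined from the documents: nil with forced answers, about 1.4% to 24% of GEC change scores at assumed independent blank rates of 0.01% to 0.2%, and about 2% to 19% if 1% to 10% of forms contain a blank. A blank in a BRI item removes GEC and BRI but leaves MI, and the reverse.

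A reader might infer that participants leave the analysis or that the primary result is affected. Neither follows. The Full Analysis Set is defined on the AISRS (SAP 5.3), so only the n of the BRIEF-A summaries shrinks. The study is single-arm, without power considerations (SAP 3.6) or formal hypotheses (SAP 5.5), and nominal p-values for secondary endpoints are optional (SAP 7.2). The cost is some precision and a possible, undemonstrated selection; no error rate or decision rule is involved. This is a low-priority improvement, not an error or a contradiction.

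**What to change.** Reword SAP 5.6.1 for BRIEF-A:

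1. If the BRIEF-A Professional Manual, which SAP 4.2 already cites for T-scores, has a missing-item rule, use that rule.
2. Otherwise prorate BRI and MI when at least 90% of the index items are answered: mean of answered items × number of items, rounded to an integer. Take GEC = BRI + MI. The 90% threshold is a convention and should be stated as one.
3. Keep the all-items rule as a sensitivity analysis.
4. State whether the nine individual scales stay under the all-items rule. Protocol 9.2.2.4 calls their T-scores secondary outcome measures. A 90% threshold gives the 6- and 8-item scales no tolerance (5/6 = 83%, 7/8 = 87.5%) and allows one blank on the 10-item scales.

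It would also help to record whether the app forces an answer to every BRIEF-A item. If it does, the new rule is never used and costs nothing.

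The change needs SAP wording only, with no new data or visits, and relies on mean-based imputation that the SAP already accepts for the ASRS and AISRS. The downside is a rounding-level imputation error in a few scores.
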